7.12 Contraception and Pregnancy

All sexually active women of childbearing potential must agree to use a highly effective method of contraception from the Screening Visit (Visit 1) throughout the study period and for 180 days following the last dose of trial drug. If using hormonal agents the same method must have been used for at least 1 month before study dosing Lactating women must agree to discontinue breast feeding before trial treatment administration.

For the purposes of this trial, a female subject of childbearing potential is a woman who has not had a hysterectomy, bilateral oophorectomy, or medically-documented ovarian failure. Women \leq 50 years of age with amenorrhea of any duration will be considered to be of childbearing potential.

Men, if not vasectomised, must agree to use barrier contraception (condom plus spermicide) during heterosexual intercourse from screening through to study completion and for 180 days from the last dose of study investigational medicinal product.

Refer to 8.1.1.6 of Study Protocol if a pregnancy is reported, either that of a female participant, or the partner of a male participant.

7.13 Patient Follow Up

7.13.1 Follow-up Visit 4 (Day 7 +/- 3 days. Week 1)

Clinical assessment

CDAID

- Vital signs (heart rate, blood pressure, oral body temperature (°C), respiratory rate, (all taken in supine position)
- Biochemistry bloods (see Section 7.8.8)
- Haematology bloods (see Section 7.8.8)
- Pharmacokinetics/Pharmacodynamics
- CDAI
- Patient Daily Diary
- Adverse Event/SAE reporting
- Record of patient concomitant medication
- Blood sample (serum) for additional research

7.13.2 Follow-up Visit 5 (Day 14 +/- 3 days. Week 2)

- Clinical assessment
- Vital signs (heart rate, blood pressure, oral body temperature (°C), respiratory rate, (all taken in supine position)
- 12 lead ECG
- Biochemistry bloods (see Section 7.8.8)
- Haematology bloods (see Section 7.8.8)
- Blood sample (serum) for additional research/Pharmacokinetics/Pharmacodynamics
- CDAI
- Patient Daily Diary
- Adverse Event/SAE reporting
- Record of patient concomitant medication

7.13.3 Follow-up Visit 6 (Day 28 +/- 3 days. Week 4)

- Clinical assessment
- Vital signs (heart rate, blood pressure, oral body temperature (°C), respiratory rate, (all taken in supine position)
- Physical examination
- Pregnancy test
- Biochemistry bloods (see Section 7.8.8)
- Haematology bloods (see Section 7.8.8)
- Pharmacokinetics/Pharmacodynamics
- CDAI
- Immunogenicity blood sample
- Patient Daily Diary
- Faecal calprotectin (patient stool sample)
- Adverse Event/SAE reporting
- Record of patient concomitant medication
- Blood sample (serum) for additional research

7.13.4 Follow-up Visit 7 (Day 56 +/- 3 days. Week 8)

- Clinical assessment to document clinical events and AEs
- Vital signs (heart rate, blood pressure, oral body temperature (°C), respiratory rate, (all taken in supine position)

CDAID

- Physical examination
- Biochemistry bloods (see Section 7.8.8)
- Haematology bloods (see Section 7.8.8)
- Pharmacokinetics/Pharmacodynamics
- CDAI
- Immunogenicity blood sample
- Patient Daily Diary
- Adverse Event/SAE reporting
- Record of patient concomitant medication
- Blood sample (serum) for additional research

7.13.5 Follow-up Visit 8 (Day 84 +/- 3 days. Week 12)

- Clinical assessment to document clinical events and AEs
- Vital signs heart rate, blood pressure, oral body temperature (°C), respiratory rate, (all taken in supine position) and weight (kg)
- Physical examination
- Pregnancy test
- Biochemistry bloods (see Section 7.8.8)
- Haematology bloods (see Section 7.8.8)
- Pharmacokinetics/Pharmacodynamics
- Endoscopy with biopsy with photographic images and/or video recordings
- CDAI
- Immunogenicity blood sample
- Patient Daily Diary
- Faecal calprotectin (patient stool sample)
- Adverse Event/SAE reporting
- Record of patient concomitant medication
- Faecal calprotectin
- Blood sample (serum) for additional research

7.13.6 Follow-up Visit 9 (Day 112 +/- 7 days. Week 16)

- Clinical assessment
- Vital signs (heart rate, blood pressure, oral body temperature (°C), respiratory rate, (all taken in supine position)
- Physical examination
- Biochemistry bloods (see Section 7.8.8)
- Haematology bloods (see Section 7.8.8)
- Pharmacodynamics
- CDAI
- Immunogenicity blood sample
- Patient Daily Diary
- Adverse Event/SAE reporting
- Record of patient concomitant medication
- Blood sample (serum) for additional research

7.13.7 Follow-up / End of Study Visit 10 (Day 168 +/- 7 days. Week 24)

- Clinical assessment
- Vital signs (heart rate, blood pressure, oral body temperature (°C), respiratory rate, (all taken in supine position)
- Pregnancy test
- 12 lead ECG
- Biochemistry bloods (see Section 7.8.8)
- Haematology bloods (see Section 7.8.8)
- Pharmacokinetics/Pharmacodynamics
- CDAI
- Immunogenicity blood sample
- Patient Daily Diary
- Faecal calprotectin (patient stool sample)
- Adverse Event/SAE reporting
- Record of patient concomitant medication
- Blood sample (serum) for additional research

NB: All visit dates / times are related to Visit 3 (Day 1). If a visit is delayed for any reason the next visit date will be scheduled in relation to Visit 3. There are no planned treatment delays. If a drug infusion visit cannot be performed within the required timeframe, every attempt should be made to administer the infusion as close as possible to the permitted time window. In extreme situations, protocol-scheduled visits may be cancelled and declared as missed visits at the clinical discretion of the Investigator.

7.14 Patient Withdrawal

The Investigator will make every reasonable effort to keep each patient on treatment. However, if the Investigator removes a patient from the study treatment or if (s)he declines further participation final assessments will be performed, if possible. All the results of the evaluations and observations, together with a description of the reasons for study withdrawal, must be recorded in the CRF.

In the event of a patient's decision to withdraw from the trial, the Investigator must ascertain from which aspects of the trial the patient wishes to withdraw, and record the details on the appropriate CRF. All patients will continue to be followed-up (if they agree), and all information and tissue samples collected up until the point of retraction, will be retained and analysed.

Patients who are removed from treatment due to adverse events (clinical or laboratory) will be treated and followed according to accepted medical practice. All pertinent information concerning the outcome of such treatment must be recorded in the CRF.

The following are justifiable reasons for the Investigator to withdraw a patient from study:

- Withdrawal of consent
- Serious violation of the trial protocol (including persistent patient attendance failure and persistent noncompliance)
- Withdrawal by the Investigator for clinical reasons not related to the study drug treatment

The maximum potential sample size, 36, has been calculated to cover patient withdrawals.

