01	13-Mar-2019	5.0	Substantial Amendment	 Schedule of Events – Information regarding endoscopy images added. Information Clarification on when Patient Daily Diary should be completed Additional information included regarding photographic images and/or video recordings in Sections 3, 5 and 7 Update of Section 6.2 Emergency Randomisation Minor typos throughout
02	12-Aug-2019	6.0	Substantial Amendment	 Reduction in sample size from 30 to 21 Removal of CDAI score from Eligibility Criteria Clarification of PK and PD sampling. EOI and 4-8hour sample for Visit 3 PD removed. Visit 9 PK removed. Clarification of screening endoscopy timepoint and biopsy samples Change to permitted concomitant medications (washout) and prohibited medications Change of SAE reporting email address Amendment to CRFs. Removal of SES-CD CRF. Inclusion of Endoscopy Score Form CRF Removal of 2nd interim analysis

TRIAL SYNOPSIS

Trial Title	A Phase Ib/IIa, Randomised, Double Blind, Placebo-Controlled Trial to Investigate the Safety, Tolerability and Clinical Activity of Humanised Antibody GSK1070806 in the Treatment of Patients with Moderate-to-Severe Crohn's Disease
Trial Design	A randomised, double-blind, placebo-controlled trial in patients with moderate-to- severe active Crohn's disease
Trial Duration	3 years (12-18 months recruitment period)
Patient Population	Adult patients with Crohn's disease
Sample Size	21

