3. TRIAL DESIGN

3.1 Discussion of Design

The proposed study will be a randomised, double blind, placebo-controlled trial to investigate the safety, tolerability, clinical activity, pharmacokinetics and pharmacodynamics of single intravenous infusion (one dose on Day 1) of GSK1070806 or placebo, in patients with active, moderate to severe CD. The primary objective of the study is to assess the safety and tolerability of a single dose IV administration of GSK1070806. A secondary objective will be to evaluate the effect of GSK1070806 in change of CDAI over time. Further secondary endpoints will include assessment of endoscopic response in patients at week 12. (Other secondary endpoints are detailed in Section 2.3).

21 patients will be recruited with randomisation of 2:1 active drug to placebo in multiple centres in the UK.

An initial screening shall take place to identify patients diagnosed with CD for at least 3 months prior to screening and colonoscopic confirmation of active mucosal inflammation (SES-CD excluding narrowed component \geq 6; or in patients with isolated ileal disease \geq 4).

Patients who do not have colonoscopically demonstrated mucosal inflammation will be excluded even if they have MRI evidence of CD more proximally in the small intestine. Colonoscopic SES-CD criteria has to be fulfilled within 28 days prior to dosing.

The induction of clinical activity will be assessed at week 12 by CDAI score, average clinical SF and/or AP scores as well as by colonoscopic assessment of baseline photographic images and/or video recordings and week 12 photographic images and/or video recordings.

The first 5 patients randomised into the trial will be dosed at least 3 days apart. At the interim analysis time point, a safety decision will be taken on the subsequent recruitment and patient spacing out strategy.

Protocol waivers or exemptions are not allowed. Therefore, adherence to the trial design requirements, including those specified in the Schedule of Events Table, are essential.

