10.4 Recruitment Period

Recruitment in the CDAID trial is estimated to take place over an approximate 12-18 month period. Due to the total number of included patients being set at 21 in total, the maximum recruitment rate required per site will be approximately one /two patients per month. With an estimated 5 new referrals per week at each site, the perception is that this target will be met without difficulty.

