12. STATISTICAL CONSIDERATIONS

The proposed analysis methods are described in Section 12.2. Success of the trial with respect to CDAI score will be defined as concluding that the mean response profile under GSK1070806 is superior (i.e. takes lower values) to that under placebo. This repeated measures analysis will be performed using a regression model. The determination of success is not attached to any particular time-point, but considers outcomes at all times. Secondary outcome measures will provide supportive evidence for the effect of GSK1070806 in patients with active CD.

Up to 21 patients will be randomised to GSK1070806 or placebo in a 2:1 ratio. The sample size has been chosen based on feasibility and practical constraints. This trial was initially conceived using a sample size of at least 30 patients. An indication of the statistical performance of the trial with n=30 using the proposed analysis method is given in Section 12.3.

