12.4 Evaluability

Patients are evaluable when they receive IMP. Inevaluable patients may be replaced.

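### Section 7.14 gives a maximum sample size of 36 that covers withdrawals; the rest of the protocol sets 21, with no stated withdrawal allowance

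*Protocol*

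**What the plan says.** Section 7.14 (Patient Withdrawal) ends with: "The maximum potential sample size, 36, has been calculated to cover patient withdrawals".

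The other current statements of size are:

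- Synopsis: sample size 21.
- Section 3.1: "21 patients will be recruited with randomisation of 2:1 active drug to placebo in multiple centres in the UK".
- Section 10.4: "Due to the total number of included patients being set at 21 in total".
- Section 12: "Up to 21 patients will be randomised to GSK1070806 or placebo in a 2:1 ratio". It gives the basis as "The sample size has been chosen based on feasibility and practical constraints" and adds the history: "This trial was initially conceived using a sample size of at least 30 patients".

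Section 12.4 makes a patient evaluable on receipt of trial drug and adds: "Inevaluable patients may be replaced". It sets no cap on replacements.

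The amendment log records "Reduction in sample size from 30 to 21". That entry is history and is not itself in conflict with anything. The conflict lies between sentences of the current body text.

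**The concern.** Section 7.14 makes two claims: that the ceiling is 36, and that this ceiling was worked out to absorb withdrawals. Neither agrees with the statistical section, where the ceiling is 21 and the basis is feasibility.

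Two things are at stake. First, this is a Phase Ib/IIa trial whose primary objective is safety, so the protocol should give one limit on how many patients may be enrolled and exposed. Second, someone reading the withdrawal section is told that attrition has been provided for. If it has not, every patient lost after dosing comes off the 21 and weakens the repeated CDAI comparison, which is the key secondary outcome.

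**Working it through.** **1. Can 36 be derived from the protocol?** A withdrawal allowance needs a base size and a rate d. The protocol gives no d, so 36 cannot be reproduced from stated inputs. Taking assumed rates and the usual formula N/(1 − d), rounded up:

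| Assumed d | Base 21 | Base 30 |
|---|---|---|
| 10% | 24 | 34 |
| 15% | 25 | 36 |
| 1/6 (16.7%) | 26 | 36 |
| 20% | 27 | 38 |

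The simpler form N × (1 + d) gives 30 × 1.2 = 36.

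From a base of 21, the rate needed is d = 1 − 21/36 = 15/36 = 41.7%. So 36 is not a plausible allowance on 21. It fits a base of 30 in at least three ways: 30/0.85 = 35.3, rounded up to 36; 30/(1 − 1/6) = 36; and 30 × 1.2 = 36.

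**2. Size of the contradiction.** 36/21 = 1.71, so the Section 7.14 figure is 71% higher. At 2:1, 21 splits into 14 active and 7 placebo, and 36 into 24 active and 12 placebo. The difference is 10 patients on active drug.

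**3. What Section 12.4 covers.** Only patients who never received trial drug are inevaluable and replaceable. A dosed patient who withdraws stays evaluable and is not replaced. Replacement can therefore make good a loss before dosing, but not one after it. If all 21 have been randomised and one is undosed, a replacement would be a 22nd randomisation, which the Section 12 limit does not allow. The number dosed still cannot exceed 21.

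**4. What uncovered losses could cost (illustration).** The inputs are the recipe in Sections 12.3.1 and 12.3.2: baseline N(285, 80²), noise SD 30, the scalars in Table 10, a random intercept with saturated time by arm, a joint test at 0.05, and a negative sum of treatment effects. The protocol leaves some details open. The version used has no noise at week 0, includes an arm term at baseline in the joint F test, and takes the sum over post-baseline visits. It was chosen because it reproduces the protocol's own figures at 10 + 20:

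| | Scen 2 | Scen 3 | Scen 4 | Scen 5 |
|---|---|---|---|---|
| Table 10, 10 + 20 | 0.928 | 0.860 | 0.851 | 0.880 |
| Reproduced, 10 + 20 | 0.925 | 0.860 | 0.848 | 0.884 |
| 7 + 14 (all 21) | 0.86 | 0.77 | 0.69 | 0.67 |
| 6 + 12 (3 of 21 lost) | 0.80 | 0.72 | 0.60 | 0.56 |
| Loss, 7 + 14 to 6 + 12 | 0.06 | 0.05 | 0.09 | 0.11 |

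Repeat runs move single entries by up to about 2 points. For example, 20,000 runs per scenario at 6 + 12 gave 0.80/0.70/0.61/0.56. The loss of 3 of 21 (14%) is an assumption, not a protocol figure.

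**The case against.** The best defence is that the practical risk is small. The governing statistical section and three other places agree on 21, and all patients are randomised centrally, so no site could recruit to 36 on the strength of Section 7.14. No endpoint or analysis changes. That stands and limits the weight of the point, but it does not make the sentence correct.

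Three stronger readings are tempting, and the documents do not support them.

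- A reader might infer that the replacement rule leaves the number exposed open. It does not. Replacement applies only to undosed patients, so the rule conflicts with the Section 12 limit on the count of randomisations alone. Only the figure of 36 contradicts the exposure limit.
- A reader might state as fact that 36 is 30 plus 20%. The arithmetic fits, but other rates fit equally well and the protocol names none. That the sentence was left over from the 30-patient design is a reasonable inference and no more.
- A reader might take the 6 + 12 row as the expected effect of withdrawals. It is a worst case. Section 7.14 keeps withdrawn patients in follow-up if they agree and retains data already collected, and Section 12.2.1 plans repeated-measures models that use partial data. Section 12.3.2 also expects the planned Bayesian analysis to perform better than the simulated one.

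**Conclusion.** The inconsistency is established from current text alone: a ceiling of 36 in Section 7.14 against 21 in the synopsis and Sections 3.1, 10.4 and 12. At 2:1 this is 24 against 14 patients on active drug. The statement that withdrawals are covered has no support for the current design, because no withdrawal rate or inflation is stated, 21 is justified by feasibility, and replacement stops at dosing.

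These conclusions do not depend on where 36 came from or on the simulation. The simulation shows only that post-dose losses could matter: about 5 to 11 points across Scenarios 2 to 5, assuming complete loss of 3 of 21 patients and the frequentist model calibrated to Table 10. This is a sample-size statement that is wrong as written. It should be corrected, but it does not invalidate the design.

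**What to change.** In Section 7.14, delete the sentence giving 36. Replace it with a statement that the sample size is 21 and includes no allowance for withdrawal after dosing.

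State in Sections 12 and 12.4 whether 21 counts randomised or dosed patients. If dosed, say that randomised but undosed patients may be replaced, up to a stated cap on randomisations. If randomised, remove the replacement option. Then use the same number, with the same meaning, in the synopsis and Sections 3.1, 7.14, 10.4, 12 and 12.4.

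The cost is a few words in the next amendment. The analysis method does not change.

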8. ADVERSE EVENT REPORTING

The collection and reporting of Adverse Events (AEs) will be in accordance with the Medicines for Human Use Clinical Trials Regulations 2004 and its subsequent amendments. Definitions of different types of AE are listed in Appendix 3. The Investigator should assess the seriousness and causality (relatedness) of all AEs experienced by the patient (this should be documented in the source data) with reference to the GSK1070806 Investigator Brochure prior to the transmission of the report to Sponsor.

8.1 Reporting Requirements

8.1.1 Adverse Events

All medical occurrences which meet the definition of an AE (see Appendix 2 for definition) should be reported. Please note this includes abnormal laboratory findings.

8.1.1.1 Pre-existing conditions

Pre-existing conditions will be collected as part of the patients' medical history on the AE Form. However, a preexisting condition will not be categorised as an AE unless the condition worsens by at least one CTC grade during the trial.

8.1.1.2 Hypersensitivity and Infusion Reactions

Hypersensitivity reactions are defined according to the NCI-CTCAE Version 4.0 definition of allergic reaction / hypersensitivity, as follows:

Grade 1: transient flushing or rash, drug fever <38°C

Grade 2: rash, flushing, urticaria, dyspnoea, drug fever ≥38°C

Grade 3: symptomatic bronchospasm, requiring parenteral medication(s), with or without urticaria; allergy-related oedema/angioedema, hypotension

Grade 4: anaphylaxis (a life-threatening event characterized by the rapid onset [often within minutes] of airway obstruction [bronchospasm, stridor, hoarseness], urticaria, and/or hypotension)

8.1.1.3 Infusion Related Reactions

Infusion-related reactions are defined according to the NCI-CTCAE Version 4.0 definition, as follows:

Grade 1: mild, transient reaction, infusion interruption not indicated; intervention not indicated

Grade 2: therapy or infusion interruption indicated but responds promptly to symptomatic treatment (for example, antihistamines, non-steroidal anti-inflammatory drugs [NSAIDS], narcotics, I.V. fluids); prophylactic medications indicated for \leq 24 hours

Grade 3: Prolonged (for example, not rapidly responsive to symptomatic medication and/or brief interruption of infusion); recurrence of symptoms following initial improvement; hospitalisation indicated for clinical sequelae

Grade 4: Life-threatening consequences; urgent intervention indicated consistent with usual medical practice, selected parenteral medications may be utilised as detailed below. Additional treatments, chosen according to clinical symptoms and local standards, may be utilised at investigator discretion.

8.1.1.4 Liver Related Toxicity : Biochemistry/LFTs

All liver related toxicity will be reported in accordance with Appendix 6 of the trial protocol using the Liver Toxicity Event Form and/or SAE form. Reporting of these events will need to be via the expedited procedure detailed in Section 8.2.1.2.

Medically significant events that need to be reported as an SAE include:

- ALT > 3xULN and total bilirubin[#] > 2xULN (>35% direct),
- or ALT > 3xULN and INR^{##} > 1.5

[#] Serum bilirubin fractionation should be performed if testing is available; if unavailable, measure urinary bilirubin via dipstick. If fractionation is unavailable and ALT > 3xULN and total bilirubin > 2xULN, then the event is still to be reported as an SAE.

^{##} For patients receiving anticoagulants INR testing is not required and the threshold value stated above does not apply.

8.1.1.5 Serious Adverse Events

Investigators should report AEs that meet the definition of an SAE (see Appendix 2 for definition).

8.1.1.6 Monitoring pregnancies for potential Serious Adverse Events

While pregnancy itself is not considered to be an AE or SAE, any pregnancy complication or elective termination of a pregnancy will be reported as an AE or SAE. A spontaneous abortion is always considered to be an SAE and will be reported as such. It is important to monitor the outcome of pregnancies (conception occurring within 6 months of study drug administration) of patients in order to provide SAE data on congenital anomalies or birth defects.

In the event that a patient or their partner becomes pregnant during the SAE reporting period please complete a Pregnancy Notification Form (providing the patient's details) and return to the CDAID Trials Office as soon as possible. If it is the patient who is pregnant provide outcome data on a follow-up Pregnancy Notification Form. Where the patient's partner is pregnant consent must first be obtained and the patient should be given a Pregnancy Release of Information Form to give to their partner. If the partner is happy to provide information on the outcome of their pregnancy they should sign the Pregnancy Release of Information Form. Once consent has been obtained provide details of the outcome of the pregnancy on a follow-up Pregnancy Notification Form. If appropriate also complete an SAE Form as detailed below.

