	 All other medications including over-the-counter medicines, supplements, vitamins and herbal remedies that each participant is taking at the time of consent will be permitted and recorded.
	See Section 7.11 for further concomitant medication information
Trials Office Contact	D3B (Diagnostics, Drug, Devices and Biomarkers) Team
Details	Cancer Research UK Clinical Trials Unit
	[name]
	Institute of Translational Medicine
	[name]
	[name]
	[name]
	Birmingham
	United Kingdom
	[name]
	☎ [name] or [name]
	≞ [name]
	⊠ [contact]

TRIAL SCHEMA

Figure 1 Trial Schema

SCHEDULE OF EVENTS

		Treatment perio	Treatment period (Week 1)			Follow-up (+/- 3 days) Days					
Schedule of Assessments	Screening per	iod	Week 1	Week 1	Week 1	Week 2	Week 4	Week 8	Week 12	Week 16	Week 24
Time schedule	Visit 1 ≤ 28 days of Randomisation	Visit 2 ≤ 7 days of Day 1	Visit 3 Day 1 (Day of Treatment)	Visit 3a Day 2 [#]	Visit 4 Day 7	Visit 5 Day 14	Visit 6 Day 28	Visit 7 Day 56	Visit 8 Day 84	Visit 9 Day 112	Visit 10 Day 168
Informed Consent	х										
Demographics (age, gender, ethnicity)	x										
Medical & Crohn's Disease History	х										
Inclusion/Exclusion criteria	х	x									
Randomisation		X (up to 7 days before Day 1 of treatment)									
Clinical Assessment ¹	х	x	x	x	x	x	х	x	x	x	х
Vital Signs ²	х	х	X ^{2a}	X	x	x	Х	х	х	x	x
Physical Examination ³	х	х	x	X			х	х	Х	x	
Serology Screening (HepB, HepC,)	х										

		Treatment perio	d (Week 1)	Follow-up (+/- 3 days) Days							
Schedule of Assessments	Screening pe	riod	Week 1	Week 1	Week 1	Week 2	Week 4	Week 8	Week 12	Week 16	Week 24
Time schedule	Visit 1 ≤ 28 days of Randomisation	Visit 2 ≤ 7 days of Day 1	Visit 3 Day 1 (Day of Treatment)	Visit 3a Day 2 [#]	Visit 4 Day 7	Visit 5 Day 14	Visit 6 Day 28	Visit 7 Day 56	Visit 8 Day 84	Visit 9 Day 112	Visit 10 Day 168
Influenza Risk Screening ⁴	x		x								
Clostridium Difficile Testing	x										
Pregnancy test	x		x				х		х		х
12 Lead ECG ⁵	x		x			х					x
Quantiferon GOLD(TB test) ⁶	x										
Biochemistry ⁷	x	х	x	x	х	х	х	х	x	х	х
Haematology ⁸	x	х	x	x	х	х	х	х	х	х	х
Pharmacokinetics ⁹			x	x	х	х	х	x	x		х
Pharmacodynamics sampling ¹⁰			x	х	х	x	x	x	x	х	x
Endoscopy with Biopsy ¹¹	x								х		
CDAI	x	х	x		х	x	х	x	x	х	x
Immunogenicity Blood sample ¹²			X (pre-dose)				x	x	x	x	x
Patient Daily Diary ¹³	x	х	X	x	х	х	х	х	х	х	Х

			Treatment period (Week 1)		Follow-up (+/- 3 days) Days						

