8.1.2 Reporting period

The reporting period for AEs will commence from the date of consent, (typically Visit 1: screening visit) and will continue until the follow-up visit (Visit 10: Day 168), The reporting period for SAE will commence from the date of consent, (typically Visit 1: screening visit) and will continue until the end of study (Visit 10: Day 168),

SAEs that are judged to be at least possibly related to the IMP must still be reported in an expedited manner irrespective of how long after IMP administration the reaction occurred.

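### Section 8.1.1.6 sets a 6-month conception window for monitoring pregnancies, but its notification rule ends at Visit 10, about two weeks sooner

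*Protocol*

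**What the plan says.** - **Aim (Protocol 8.1.1.6, first paragraph).** Outcomes of patients' pregnancies are to be monitored, to supply SAE data on congenital anomalies and birth defects. The window is "conception occurring within 6 months of study drug administration".
- **Instruction to sites (8.1.1.6, second paragraph).** "In the event that a patient or their partner becomes pregnant during the SAE reporting period please complete a Pregnancy Notification Form". Partners of male patients first appear here.
- **End of the SAE reporting period (8.1.2).** SAE reporting starts at consent and "will continue until the end of study (Visit 10: Day 168". The same section keeps SAEs with at least a possible link to the study drug reportable without a time limit.
- **Timing of Visit 10 (7.13.7).** "Day 168 +/- 7 days. Week 24". The Schedule of Events carries a different header, "Follow-up (+/- 3 days) Days", and its note sends the reader to the sections for visit windows.
- **Last test (7.13.7).** The Visit 10 list includes "Pregnancy test". No later test or contact is planned, and Section 11 ends the trial at the last patient's last visit.
- **Contraception (4.1 and 7.12).** For women Section 7.12 requires it "for 180 days following the last dose of trial drug". Men have the same 180 days.

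**The concern.** Two adjacent paragraphs of one section set different windows. The first says which pregnancies matter, and the second says which ones the site must notify. The second window closes first, so a conception on Day 176, for example, belongs to the group to be monitored but triggers no form, even if Visit 10 was held as late as allowed.

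Section 8.1.1.6 also says that pregnancy itself is neither an AE nor an SAE, so the ordinary reporting rules do not pick it up. A partner of a male patient is never tested, so notice of a partner pregnancy depends on this rule alone.

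At stake is the completeness of exposure data for a drug that, per Section 1.1.7, had been given to 89 participants, in a trial whose primary objective is safety.

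**Working it through.** This is day arithmetic. No sample size, power or error rate is involved.

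**Inputs.** Visit 10 at Week 24, +/- 7 days (7.13.7). SAE reporting ends at Visit 10, Day 168 (8.1.2). Contraception for 180 days (4.1, 7.12). Conception window of 6 months (8.1.1.6), taken as 182 days.

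**Step 1, the plan's own figure.** 24 x 7 = 168, so Day 168 is reproduced. With the visit window, Visit 10 falls between 168 - 7 = Day 161 and 168 + 7 = Day 175.

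**Step 2, the uncovered interval.** Gap = end of the exposure window minus the day of Visit 10.

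| Visit 10 held on | Gap to 180 days | Gap to 6 months (182 days) |
|---|---|---|
| Day 161 | 180 - 161 = 19 | 182 - 161 = 21 |
| Day 168 | 180 - 168 = 12 | 182 - 168 = 14 |
| Day 175 | 180 - 175 = 5 | 182 - 175 = 7 |

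**Step 3, sensitivity to the reading.**
- Six calendar months last 181 to 184 days. The gap at Day 168 is then 13 to 16 days, and the full range is 181 - 175 = 6 to 184 - 161 = 23 days.
- With the schedule header's +/- 3 days (Day 165 to Day 171), the gap to 180 days is 180 - 171 = 9 to 180 - 165 = 15 days.
- If dosing is counted as Day 1, then Day 168 is 167 days after the dose, and each gap grows by one day.

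The gap is positive under every reading.

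**Step 4, how many events this could involve.** Appendix 5 defines the listed methods for women as failing in under 1% of users per year. Assume, as an upper limit, that all 21 patients are women of childbearing potential. Expected conceptions in the gap are then below 21 x (14/365) x 0.01 = 0.008, or 21 x (21/365) x 0.01 = 0.012 for the 21-day gap. This assumes consistent use and applies the same rate to the two days after Day 180. It does not cover partners, because the protocol gives no failure rate for the method required of men.

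**The case against.** The best case for the protocol is that its other provisions leave little uncovered.

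- Table 9 asks for the Pregnancy Notification form within 24 hours of the site learning of a pregnancy, with no end date. This sits awkwardly with a hard stop at Day 168, but it sets speed of reporting and does not extend the period named in 8.1.1.6.
- Congenital anomalies are SAEs under Appendix 2, and miscarriages always are under 8.1.1.6. Those with at least a possible link to the drug stay reportable under 8.1.2 without limit. This stands. It leaves out outcomes judged unrelated and uncomplicated pregnancies, and it works only if the site happens to hear of the event.
- Very few events are expected, as the bound above shows. This stands too, and it governs the weight of the point.

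Three stronger readings are tempting, and the documents do not support them.

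- A reader might infer that late pregnancies are lost to the sponsor. The open-ended rule for related SAEs rules that out. What can be said is that they are not solicited.
- A reader might add a lag before a test turns positive and so lengthen the gap. But the trigger is becoming pregnant in the period, not being found pregnant in it. A conception shortly before Visit 10 is already inside the rule. Late recognition is a matter of detection, and any figure for it needs a lag that the protocol does not give.
- A reader might argue from the plasma occupancy figures in Section 1.2.3 that drug effect persists past Visit 10. The protocol states no half-life, and those figures concern IL-18 suppression, not fetal exposure. The point does not need them.

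The 6-month sentence also speaks of patients' pregnancies. It cannot be read as already setting a 6-month window for partners.

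**Conclusion.** The contradiction within Section 8.1.1.6 holds as written. The notification rule ends 12 days (5 to 19) short of the 180-day contraception period and about 14 days (7 to 21) short of the 6-month window. This rests on Visit 10 marking the end of SAE reporting, the +/- 7 days of Section 7.13.7, and 6 months taken as 182 days. Changing the last two alters the size of the gap but does not close it.

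The consequence is limited: pregnancies conceived in that interval are not asked about, and their outcomes reach the trial only through the related-SAE route. With at most 21 patients under a 180-day contraception requirement, this is a minor inconsistency in safety reporting with no bearing on any efficacy or safety analysis. It is worth correcting because the correction is nearly free.

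**What to change.** - **8.1.1.6.** End the notification rule at the conception window the section already states (within 6 months of study drug) in place of the end of the SAE reporting period. Keep the present start at consent, so that nothing now covered drops out. Say explicitly whether the window applies to partners as well as patients; the 180-day contraception rule for men supports including them.
- **8.1.2.** State that pregnancy notification and outcome follow-up continue past Visit 10.
- **Visit 10.** Ask patients to tell the site of any later pregnancy conceived within that window.
- **Visit window.** Reconcile the Schedule of Events header with Section 7.13.7, so that the end of the SAE reporting period is unambiguous.

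The cost is about two sentences of protocol text, a line in the patient information and a reminder at a visit that already takes place. For pregnancies covered by the revised rule, the uncovered interval falls to zero days.
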